8.7. Screening Assessments

See [Table 4](#) for the list of assessments that are routine plasma donor screening and/or testing assessments and those that are considered part the clinical trial data that will be reported on an eCRF and will be included in the data analysis and final clinical study report.

After signing informed consent to the study, subject screening for eligibility will occur over a 7-day period (Study Days -7 to -1). The following procedures will be performed to assess subject eligibility and to collect other baseline or plasma donor suitability screening data:

- Demographics
- Medical history
- Immunization record and medications used within the past 7-days
- Pre-donation screening examination including:
 - Agree to contraceptive use for women of child-bearing potential for the duration of the study
 - Vital signs
 - Infectious disease screening of donor plasma, tetanus antibody test of donor plasma, hematocrit and total protein
 - Full physical examination for new donors (this is waved for donors of record who have had a full physical examination during the last year)
- Body weight
- Review eligibility checklist

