5.1. Safety Endpoints

Adverse Events: AEs will include any treatment emergent unfavorable and unintended sign or symptom including abnormal laboratory findings that occur at any time after the subject has signed informed consent until the second follow up visit after the last study vaccination, whether or not considered drug related.

Severity: All AEs will be assessed for severity by the investigator. Assignment of grade based on the intensity of symptoms and the degree of limitation of usual daily activities will be done according to severity using the following criteria:

Mild: The AE did not cause interference with the subject's activity.

Moderate: The AE produced limited functional impairment and may have required therapeutic intervention. The AE produced no sequelae.

Severe: The AE resulted in significant impairment of function and may have lead to temporary inability to resume the subject's normal life pattern.

Relationship: The degree of certainty for which the AE/SAE is attributed to the investigational product or alternative causes will be determined by the investigator's use of clinical judgment in conjunction with the assessment of a plausible biologic mechanism, a temporal relationship between the onset of the event in relation to receipt of the investigational product, and identification of possible alternate etiologies including underlying disease, concurrent illness or concomitant medications. Only a physician can make this determination.

The following drug relationships will be used for this clinical study:

Unrelated: There is no temporal relationship between the event and the administration of the product or the event is clearly due to the subject's medical condition, other therapies, or accident.

Unlikely: There is evidence of exposure to the product but there is another more likely cause of the event.

Possible: There is some temporal relationship between the event and the administration of the product and the event is unlikely to be explained by the subject's medical condition or other therapies.

Probable: The temporal relationship between the event and the administration of the product is compelling, and the subject's medical condition and other therapies cannot explain the event.

Definite: The event follows a reasonable temporal sequence from administration of the medication or follows a known or suspected response pattern to the medication.

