9.4. Immunizations, Prior and Concomitant Medications

Prior and concomitant medications will be listed by subject. Medications and treatments with an end date prior to the first dose of study drug will be considered prior medications and will be noted in listing. If the date is partial or unknown, then medication will be considered as concomitant. Any prior immunizations will be listed by subject.

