9.5. Analysis of Safety Endpoints

Treatment emergence will be evaluated for all AEs. Treatment-emergent adverse events (TEAEs) are those that occur on or after the same date and time of first dose of study drug. TEAEs will be coded using the most recent version of the Medical Dictionary of Regulatory Affairs (MedDRA) by assigning a preferred term and will be grouped by system, organ, and class (SOC) designation. AEs occurring after each vaccination up to the time of the next vaccination and separately over the whole study period will be summarized. Separate tables will be provided for solicited AEs reported within the 3 day period after each vaccination.

Each AE will be counted once only by preferred term for a given study subject within each post vaccination time period prior to the next vaccination or up to the 6-month follow-up visit after the last vaccination. If the same AE occurred on multiple occasions, the highest severity and relationship to investigational product will be assumed within each time period.

The summary tables will include an overall summary of number and percentage of subjects reporting each TEAE, summary by relationship, summary by severity will be presented by each vaccination period and overall.

Listings of each individual AE including start date, stop date, severity, relationship, duration, outcome, and actions taken will be provided.

Reactogenicity is defined as the total count of a set of solicited AEs that are expected after a vaccine. A regression analysis will be performed with reactogenicity as the dependent variable and anti-diphtheria titers as the independent variable to determine if there is an association. Anti-diphtheria titer is not expected to be normally distributed and will be natural log transformed. Null Hypothesis of no association between reactogenicity and anti-diphtheria titers will be tested on

Slope obtained using simple linear regression analysis at alpha=0.01 using two-sided tests. The null hypothesis states that the slope is equal to zero, and the alternative hypothesis states that the slope is not equal to zero. No adjustment for covariates will be made. The following SAS procedure PROC REG may be used.

```
Proc reg data=data;
Model reactogenicity =log(anti_diphtheria_titers);
Run;
```

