9.7. Analysis of Efficacy Endpoints

Tetanus antibody titers (IU/mL) will be presented as geometric mean (GeoMean), minimum and maximum concentrations after each vaccination at all collection time points. Linear plots of the geometric mean \pm Standard errors of Tetanus antibody titers will be provided by each collection time points.

The numbers and percentages of subjects whose post vaccination anti-tetanus antibody levels are <5 IU/mL; \geq 5 IU/mL to 10 IU/mL; >10 IU/mL to 15 IU/mL; and, >15 IU/mL will be presented in a table over time. The percentages of subjects in each of these categories will also be presented in scatter plot over collection time.

10. Handling of Missing Data and Missing Date

Missing Data will not be imputed.

Missing dates are handled as follows:

- Missing day: The first day of the month will be used.
- Missing Month: The first month of the year will be used.
- Completely missing dates will remain missing, with no imputation applied. Consequently, time to onset and duration of such events will be missing.

11. Validation of Programming Code

All SAS code used to generate tables, listings, and figures will be validated and reviewed before being finalized. The validation process will be used to determine that the numbers are produced by a statistically valid method and that the execution of the computations is correct. Qualified personnel who have not previously been involved in the production of the original programming code will perform the validation procedures. Methods of validation include independent programming and comparison to data listings. Tables will be reviewed for accuracy, consistency with this plan, consistency within tables, and consistency with corresponding output. Once validation is complete, a quality control reviewer will perform a final review of the documents for accuracy and consistency. Upon completion of validation and quality review procedures, all documentation will be collected and filed in the study documentation files at Fast-Track.

12. Changes to Planned Analyses

There are no changes between protocol-defined statistical analyses and those presented in this SAP.

13. Appendix A: Table and Figure Shells

List of Tables and Figures

Table 1:	Summary of Subject Disposition – All Consented Subjects	17
Table 2:	Reasons for Not Meeting Eligibility Criterion – Not Enrolled Subjects	18
Table 3:	Demographics and Subject Characteristics	19
Table 4:	Summary of Protocol and Treatment Compliance	20

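### SAP section 10 sets partial AE onset dates to the 1st of the month or to January, which can date a post-dose event before its dose; the expected effect is small and the fix is cheap

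*SAP*

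**What the plan says.** SAP section 10 has one rule for incomplete dates: "Missing day: The first day of the month will be used" and "Missing Month: The first month of the year will be used". Wholly missing dates stay missing. AE dates are in scope, because the same list adds "Consequently, time to onset and duration of such events will be missing".

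SAP section 9.5 makes onset decide two things.

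- TEAE status: "Treatment-emergent adverse events (TEAEs) are those that occur on or after the same date and time of first dose of study drug".
- The dose interval: "AEs occurring after each vaccination up to the time of the next vaccination and separately over the whole study period will be summarized". Tables 6 to 9 have one column per vaccination.

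Neither section says how a partial AE date is to be classified. For medications SAP section 9.4 does: "If the date is partial or unknown, then medication will be considered as concomitant".

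**The concern.** The rule takes no account of when the subject was vaccinated, and it can only move an onset earlier.

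- **Dose 1, day missing.** An event later in the dose month is dated before the dose and is no longer a TEAE. Some of these events are dated before day -7, although the protocol (section 8.7) says "subject screening for eligibility will occur over a 7-day period (Study Days -7 to -1"). They then fall before the AE period of SAP section 5.1, which covers events "that occur at any time after the subject has signed informed consent until the second follow up visit after the last study vaccination".
- **Doses 2 to 5, day missing.** The event stays a TEAE but is counted one column back. Dose 5 can lose events and cannot gain any.
- **Day and month missing.** With the date set to 1 January, events after doses 1 to 4 can leave the TEAE count, and events after doses 3 to 5 can move back more than one column.
- **Stop dates.** The same rule can place the end of an event before its start.

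Safety by vaccination interval and overall is the primary objective, and the study exists to examine dosing more often than licensed. A rule whose error can only lower the TEAE total and the last-dose column is anti-conservative for that purpose.

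**Working it through.** The plan states no figure on this point, so there is nothing to reproduce.

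**Inputs from the documents:** doses at months 0, 3, 6, 9 and 12; end of follow-up at month 18; the imputation rule of SAP section 10; the allocation rules of SAP section 9.5.

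**Assumed:** the timing of onset, the share of AEs with a partial date, and the number of AEs.

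**Only the day missing.** Take 30-day months, a dose on day m of the month and onset d days later. The event is misplaced when m is at least 2 and m + d is at most 30, which holds for 29 - d values of m (for d up to 29).

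| Onset after the dose | Formula | Misplaced |
|---|---|---|
| 0-3 days | (29+28+27+26)/(4 x 30) = 110/120 | 92% |
| 0-14 days | (15 x 29 - 105)/(15 x 30) = 330/450 | 73% |
| Even over 3 months (doses 1-4) | 435/(90 x 30) = 435/2,700 | 16.1% |
| Even over 6 months (dose 5) | 435/(180 x 30) = 435/5,400 | 8.1% |

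Over the whole study, 5 x 435/(4 x 2,700 + 5,400) = 2,175/16,200 = 13.4% are misplaced. Loss of TEAE status comes from dose 1 only: 435/16,200 = 2.7%. Enumerating 365 dose 1 dates on a real calendar gives 92%, 74%, 16%, 8%, 13.4% and 2.7%.

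**Dose 1 events dated before day -7.** This needs m of at least 9, which leaves 22 - d values of m. The shares are 82/120 = 68%, 225/450 = 50% and 253/2,700 = 9%. The real calendar gives 69%, 51% and 9%.

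**Day and month missing** (set to 1 January; real calendar; onset 0-14 days after the dose; dose 1 dates spread over a full year):

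| Dose | Leaves the TEAE count | Stays a TEAE but moves back more than one column |
|---|---|---|
| 1 | 98% | - |
| 2 | 73% | - |
| 3 | 48% | 25% |
| 4 | 23% | 50% |
| 5 | 0% | 73% |

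The protocol synopsis plans about 4 months of recruitment. Over the twelve possible 4-month windows, TEAE loss runs from 93% to 100% for dose 1, 20% to 100% for dose 2, 0% to 100% for dose 3 and 0% to 68% for dose 4. These shares therefore depend on the calendar months of recruitment.

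**Expected counts.** Let p be the share of AEs lacking only the day, assumed to be 1% to 10%. Assume 50 unsolicited AEs per 3 months, spread evenly, hence 100 after dose 5 and 300 in all.

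- Dose 5 column loses 0.080 x p x 100: 0.08 at p = 1%, 0.80 at p = 10%.
- Overall TEAE count loses 0.161 x p x 50: 0.08 at p = 1%, 0.81 at p = 10%.
- Columns 1 to 4 lose and gain about equally.

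**The case against.** The strongest reply is that the effect is negligible and partly inferred.

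1. **The link is not spelled out.** The SAP never says that the imputed date drives TEAE status or the dose column. Listing 11 carries a TEAE and vaccine number field whose source is not stated. This stands as a caution, but the SAP offers no other route: section 9.5 classifies by time of occurrence, and section 10 supplies the date. For solicited AEs the separate vaccination number in Listing 12 suggests that the diary card governs, so the exposure lies mainly with unsolicited events.
2. **Partial dates should be rare where they matter.** Subjects are asked about AEs before they leave after each vaccination, keep a daily diary, are due back 1 to 3 days after each dose and have monthly diary reviews. The 92% and 74% apply only to events already lacking the day, and early reactions are the best-dated events. This stands, and it is why the point is minor.
3. **Little hangs on a shifted event.** The analysis is descriptive, with no planned test between doses. The dose 5 column covers 6 months against 3 for the others. Table 8 counts a subject once per preferred term, so a shift need not change a cell. Listing 11 still shows every AE. This also stands.
4. **The remedy exchanges one error for another.** In periods 1 to 4 it does, as set out under the fix. What differs is the direction: the present rule can remove post-dose events from the TEAE count.

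**Conclusion.** The concern holds and is minor. Read with section 9.5, SAP section 10 gives a wrong placement for a definable class of AEs, and no override exists of the kind section 9.4 provides for medications. This is a stated rule with a one-directional error, not merely a missing detail.

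For a single early post-dose event lacking its day, misplacement is the likely result. For the tables as a whole, the expected effect is one event or fewer. That estimate rests on an assumed 1% to 10% of AEs lacking the day, an assumed 50 unsolicited AEs per 3 months and evenly spread onset; the documents give none of these. Dates lacking both day and month would do more damage per event but should be rare under monthly review.

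**What to change.** Add an AE-specific rule to SAP section 10:

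- **Partial onset date.** If the known part is compatible with a vaccination, impute that vaccination date, unless the stop date, diary or reporting visit shows an earlier onset. If the month is missing, use the latest vaccination that fits both the known year and the visit at which the AE was first reported. Otherwise use the first day, but never before consent.
- **Wholly missing onset.** Treat as a TEAE and assign by reporting visit, unless other data show onset before dose 1.
- **Partial stop date.** Use the last day of the month or year, capped at last contact and never before onset.

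The cost is a few lines of text and programming before database lock, with no new data.

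There is a trade-off. With only the day missing, even onset and no other evidence, the 16.1% backward error in periods 1 to 4 becomes a 16.1% forward error, and dose 5 goes from 8% misplaced to none. Overall misplacement becomes 4 x 435/16,200 = 10.7%, all forward, against 13.4%, all backward. Dose 5 would gain about 0.161 x 0.10 x 50 = 0.8 events from period 4 at a 10% partial-date rate. About 87% of day-missing events on days -7 to -1 would be counted as TEAEs (30-day months: 182/210). In return, no post-dose event with only the day missing leaves the TEAE count, and early post-dose events lacking only the day are placed correctly.
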